- Difference in plasma BNP between mHealth intervention or no intervention and/or metformin or placebo groups at week 12.
- Difference in quadriceps skeletal muscle triglyceride content between mHealth intervention or no intervention and/or metformin or placebo groups at week 12.
- Difference in change of quadriceps skeletal muscle fatigue between mHealth intervention or no intervention and/or metformin or placebo groups at week 12.
- Difference in quadriceps skeletal muscle strength between mHealth intervention or no intervention and/or metformin or placebo groups at week 12.
- Difference in quadriceps skeletal muscle contractile tissue cross-sectional area between mHealth intervention or no intervention and/or metformin or placebo groups at week 12.

- Difference in RV myocardial muscle triglyceride content between mHealth intervention or no intervention and/or metformin or placebo groups at week 12.
- Difference in tricuspid annular plane systolic excursion (TAPSE) between mHealth intervention or no intervention and/or metformin or placebo groups at week 12.
- Difference in RV and LV ejection fraction between mHealth intervention or no intervention and/or metformin or placebo groups at week 12.
- Difference in RV fractional area change between mHealth intervention or no intervention and/or metformin or placebo groups at week 12.
- Difference in tricuspid annular velocity (S') between mHealth intervention or no intervention and/or metformin or placebo groups at week 12.
- Difference in tricuspid regurgitant (TR) velocity between mHealth intervention or no intervention and/or metformin or placebo groups at week 12.
- Difference in estimated RV and RA pressure between mHealth intervention or no intervention and/or metformin or placebo groups at week 12.
- Difference in estimated RV and LV diastolic function between mHealth intervention or no intervention and/or metformin or placebo groups at week 12.
- Difference in RV free wall longitudinal strain between mHealth intervention or no intervention and/or metformin or placebo groups at week 12.
- Difference in screening clinical characteristics between responders and non-responders to mHealth intervention or no intervention and/or metformin or placebo groups at week 12.
- Difference in screening plasma metabolomics profiles, including all amino acids and lipidomics, between responders and non-responders to the mHealth intervention or no intervention and/or metformin or placebo groups at week 12.

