1.22.8 Blood Biomarkers

a. HOMA-IR

Insulin resistance will be quantified using the homeostatic model assessment of insulin resistance (HOMA-IR), which estimates insulin resistance through fasting plasma insulin and glucose ratios, at screening and 12 weeks.

b. Lipid Metabolism

Altered lipid metabolism reflects insulin resistance. Fasting plasma lipid metabolites will be evaluated via non-targeted metabolomics screen. Mass spectroscopy of approximately 300 metabolites across all major metabolic pathways will be performed at screening and 12 weeks.

c. Fatty Acid Metabolism

Elevated circulating fatty acids and acylcarnitines contribute to RV lipotoxicity and indicate insulin resistance associated with pulmonary hypertension. To evaluate the effect of this intervention on fatty acid metabolism, we will measure fasting long-chain fatty acid and acylcarnitine profiles using mass spectrometry at screening and 12 weeks.

d. Plasma and Urine Estradiol and Estrogen Metabolites

Estrogen metabolites are associated with pulmonary hypertension in human PAH subjects. Estrogen metabolism we will be evaluated by measuring plasma estradiol (E2) and estrogen metabolites, including 2ME and 16 α OHE, using mass spectrometry at screening and 12 weeks.

e. Plasma NT-proBNP

Plasma NT-proBNP reflects right ventricular function in PAH and is a strong predictor of outcome in PAH. BNP will be assessed at screening and 12 weeks.

f. Amino Acids and Metabolomics

We and others have observed in cross-sectional studies that PAH is associated with insulin resistance and lipid abnormalities. Metabolites associated with insulin resistance and lipid metabolism have not been examined in the context of a clinical trial targeting insulin resistance. Changes in amino acids and metabolomic profiles with metformin and physical activity may provide insight into the mechanisms by which these interventions may improve insulin resistance (and outcomes) in patients with PAH.

g. Safety Labs

A comprehensive panel, complete blood count, hemoglobin A1c, and a urine pregnancy test will be assessed at screening and 12 weeks.

1.22.9 *Transthoracic Echocardiographic Measures*

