1.24 Statistical Analysis

The primary analyses will focus on metformin vs placebo, exercise vs placebo, and metformin + exercise vs placebo comparisons on the primary endpoint. Since the evaluation of metformin or exercise will be reported as if they were independent studies and the combination arm versus placebo comparison serves to corroborate findings of the two separate comparisons, in addition to evaluating an additive or synergistic effect, we will not adjust for multiple comparisons. For binary endpoints, the Pearson chi-square or Fischer's exact test will be used to assess between treatment arms difference. Logistic regressions will be conducted to examine the treatment effect while adjusting for important covariates such as baseline 6MWD, functional status, age, and study site. Model over-fitting will be avoided by considering the number of parameters in the model and the number of responders in the sample. Continuous endpoints will be analyzed using either two-sample t-test or ANOVA, or non-parametric methods Wilcoxon Rank Sum test or Kruskal-Wallis test. Multivariable regressions (general linear models) will be conducted to examine the treatment effect while adjusting for important covariates such as baseline 6MWD, functional status, age, and study site. We have designed the study to minimize the potential for missing data. Subjects who drop out will be replaced up to a total of 35 per group. Nevertheless, in the event we have missing data, a multiple-imputation procedure as implemented in the aregImpute function in the Hmisc package in R (R Package; Version 3.0-10) will be used to assess the impact of missing data. The analyses with imputation will mainly serve as sensitivity analyses.

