1.26 Statistical Power

The pivotal trial of Iloprost demonstrated that in the Iloprost arm nearly 40% had 10% improvement in 6MWD, 50% had improved FC, and 17% had both¹. From these data we calculate that 73% had either 10% improvement in 6MWD or improved functional status. Assuming metformin or the exercise arm will have similar response rate, and the placebo group will have 40% response rate, thought to be due to training effect potentially, we need 35 per group to have 80% power at 0.05 type I error rate. For the metformin and exercise combination group, an additive or synergistic effect between the two interventions will put its response rate above 73%. Thus, the combination vs. placebo comparison will have at least 80%, likely better power. From past experience coupled with the low risk, low side effect profile interventions, we estimate a dropout rate of less than 10%¹. We will enroll 40 subjects to ensure 35 completed subjects per group. The total target enrollment is 160 over 4.5 years.

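### No error-rate control is specified for about 300 metabolites: at an unadjusted 0.05, up to about 15 false positives are expected per full-panel comparison

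*Combined protocol and SAP*

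**What the plan says.** Section 1.22.8(b) evaluates lipid metabolism with a non-targeted metabolomics screen: "Mass spectroscopy of approximately 300 metabolites across all major metabolic pathways will be performed at screening and 12 weeks". Section 1.22.8(f) adds that changes in amino acids and metabolomic profiles under metformin and activity may shed light on mechanism.

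The Secondary Endpoints list in the Protocol Summary uses these data in two ways:

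- Between arms: plasma lipid, free fatty acid and acylcarnitine profiles at week 12.
- By response: "Difference in screening plasma metabolomics profiles, including all amino acids and lipidomics, between responders and non-responders", followed by the capacity of metabolomic profiles at screening, and of their change, to predict response.

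No metabolomics-specific analysis is given. The general rule in section 1.24 is: "Continuous endpoints will be analyzed using either two-sample t-test or ANOVA, or non-parametric methods Wilcoxon Rank Sum test or Kruskal-Wallis test". General linear models adjusted for baseline 6MWD, functional status, age and site are also specified. The only statement on multiplicity is "we will not adjust for multiple comparisons". The reason given is that metformin and exercise will be reported as if they were independent studies, with the combination arm as corroboration.

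Section 1.22.12 derives responder markers from the separate metformin pilot, with profiling of a similar number of metabolites, and then says they will be validated and their predictive capacity tested. The third aim in the Abstract likewise speaks of prospective testing of blood markers.

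**The concern.** The argument for leaving the three primary contrasts unadjusted is that two interventions are being studied side by side. It gives no reason for leaving hundreds of parallel tests on one set of blood samples unadjusted, and nothing else in the plan fills the gap. ANOVA or an adjusted linear model does not help, because each still produces one p-value per metabolite.

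The metabolite results carry weight. They support the account of how the interventions work, and they feed the stated goal of finding which patients benefit. Without a prespecified rule, a reader of the final report cannot tell how much of a list of changed metabolites, or of responder markers, is chance.

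**Working it through.** **Inputs**

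- Metabolites: m = 300, approximate (section 1.22.8).
- Per-test level: 0.05. Section 1.26 states this for the primary endpoint only; applying it to metabolites is an assumption. Two-sided testing is also assumed.
- Completers: 35 per arm, 140 in all (section 1.26).
- Share of metabolites that truly differ, and by how much: not in the documents, so ranges are shown.

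**The plan's own figure.** Section 1.26 says "we need 35 per group to have 80% power at 0.05 type I error rate". The inputs are that "73% had either 10% improvement in 6MWD or improved functional status" and that "the placebo group will have 40% response rate". The union is 0.40 + 0.50 − 0.17 = 0.73. With pooled variance, two-sided, and mean rate (0.40 + 0.73)/2 = 0.565:

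n = [1.960 × √(2 × 0.565 × 0.435) + 0.842 × √(0.40 × 0.60 + 0.73 × 0.27)]² / 0.33² = 34.2, so 35 per group.

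The figure reproduces. A one-sided test would give 27, which supports reading 0.05 as two-sided. The plan gives no corresponding calculation for metabolites.

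**Expected false positives in one full-panel comparison.** The formula is m × (share truly null) × 0.05.

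| Truly different | Expected false positives |
|---|---|
| 0% | 300 × 0.05 = 15.0 |
| 10% | 270 × 0.05 = 13.5 |
| 20% | 240 × 0.05 = 12.0 |
| 50% | 150 × 0.05 = 7.5 |

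If none differ and tests are independent, the central 95% range is 8 to 23, and the chance of at least one false positive is 1 − 0.95^300, above 0.999999. Correlation leaves the mean alone and widens the spread. In simulation with blocks of 10 metabolites, the mean stayed at 15.0 while the SD was 3.8, 4.5 and 6.4 at within-block correlations of 0, 0.3 and 0.6.

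**False share of the flagged list, 35 v 35, unadjusted 0.05.** Power is 0.552 for a true difference of 0.5 SD and 0.917 for 0.8 SD. Both effect sizes are assumptions.

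| Truly different | False flags | True flags, 0.5 SD | False share | True flags, 0.8 SD | False share |
|---|---|---|---|---|---|
| 5% | 14.25 | 8.3 | 63% | 13.8 | 51% |
| 10% | 13.5 | 16.6 | 45% | 27.5 | 33% |
| 20% | 12.0 | 33.1 | 27% | 55.0 | 18% |

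**Effect of the pilot-to-trial step.** If a fixed list is chosen in the pilot at 0.05 and each marker is retested in the trial at 0.05, the expected number of null markers passing both is 300 × 0.05 × 0.05 = 0.75. Requiring the same direction gives 300 × 0.05 × 0.025 = 0.375.

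**Effect of adjustment.** Benjamini-Hochberg at 5% compares the k-th smallest p-value with k × 0.05/300: 0.000167 for the first, 0.00167 for the 10th, 0.005 for the 30th. The strictest case is Bonferroni at 0.05/300 = 0.000167. It raises the difference detectable with 80% power at 35 v 35 from (1.960 + 0.842) × √(2/35) = 0.67 SD to 1.10 SD. For responders against non-responders, the plan's rates imply 0.40 × 35 + 0.73 × 105 = 90.65, so about 91 v 49, and the detectable difference rises from 0.50 to 0.81 SD. Benjamini-Hochberg costs no more than this, and less as more metabolites truly differ.

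**The case against.** The strongest reply is that the plan has a discovery-and-validation design. Responder markers come from separate pilot patients and are then tested in the trial, which would leave under one null marker on the arithmetic above. That stands for markers taken by that route, provided a fixed list goes forward under a stated rule. The plan states no selection threshold, validation level or locked list, and section 1.6 reports only 16 pilot patients enrolled when it was written. The route also does not cover the between-arm profile endpoints or the trial's own responder comparison.

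Three stronger readings are tempting but not supported:

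- A reader might infer that all 300 metabolites are tested in each of the three arm contrasts, giving 45 expected false positives, or 60 with the responder comparison. The listed between-arm endpoints name lipid, free fatty acid and acylcarnitine profiles. Section 1.22.8(f) mentions metabolomic change without attaching a test. The number of lipid species within the screen is not given, so 45 and 60 are upper figures only.
- A reader might infer that the reported lists would be mostly or wholly noise. That depends on how many metabolites differ and by how much. In the scenarios above the false share runs from 18% to 63%.
- A reader might infer that the plan refuses adjustment for metabolites. The no-adjustment sentence is argued for the primary contrasts; on metabolites the plan is silent.

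It is also fair to say that these are secondary, largely mechanistic analyses in a Phase II trial, and that false discovery rate control is one reasonable choice among several. That limits how serious the gap is, but gives no reason to leave the rule unstated.

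**Conclusion.** The point holds as a gap in the secondary analyses. Followed as written, the plan would test a panel of about 300 metabolites variable by variable with no error-rate control. The size is up to about 15 expected false positives in any full-panel comparison. This rests on three assumptions: a two-sided per-test level of 0.05, the whole panel being tested, and no true differences. Fifteen is therefore a ceiling on the expectation. The exposure is clearest for the responder comparison, where the whole metabolome is a listed endpoint. It is smaller by an unknown amount for the between-arm profiles, and smallest for markers that pass through a properly locked pilot-to-trial validation. The primary endpoint and the sample size are not affected.

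**What to change.** Add to section 1.24: metabolomic, lipid, fatty acid and acylcarnitine profile endpoints will be tested with Benjamini-Hochberg false discovery rate control (for example at 5%) across all metabolites within each contrast. Q-values will be reported, and nominal p-values will be labelled descriptive.

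Add to section 1.22.12: the rule for selecting markers in the pilot, the level at which they are tested in the trial, and a commitment to lock the list before trial outcomes are examined. Markers should not be selected and evaluated on the same trial subjects. In particular, metabolites that pass the threshold in a trial contrast should not be carried into a prediction model assessed on those same subjects, because that would undo the independent validation the section intends.

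The cost is a few sentences and a routine computation. Fewer individual metabolites will be declared, and the smallest effects will be harder to call; the Bonferroni figures above bound that loss. Nothing in the primary analysis, data collection or sample size changes.

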- Composite endpoint of 10% or greater improvement in six minute walk distance over baseline or improvement of at least one WHO functional class at week 12.

SECONDARY ENDPOINTS:

- Difference in body weight between mHealth intervention or no intervention and/or metformin or placebo groups at week 12.
- Difference in BMI between mHealth intervention or no intervention and/or metformin or placebo groups at week 12.
- Difference in absolute 6MWD between mHealth intervention or no intervention and/or metformin or placebo groups at week 12.
- Difference in Borg Dyspnea Score between mHealth intervention or no intervention and/or metformin or placebo groups at week 12.
- Difference in emPHasis-10 quality of life survey score between mHealth intervention or no intervention and/or metformin or placebo groups at week 12.
- Difference in WHO functional classification between mHealth intervention or no intervention and/or metformin or placebo groups at week 12.
- Difference in average daily step count between mHealth intervention or no intervention and/or metformin or placebo groups at week 12.
- Difference in frequency of daily goal attainment between mHealth intervention or no intervention and/or metformin or placebo groups at week 12.
- Difference in daily goal aerobic time between mHealth intervention or no intervention and/or metformin or placebo groups at week 12.

- Difference in total daily activity between mHealth intervention and/or metformin and no intervention and/or metformin or placebo groups at week 12.
- Difference in resting heart rate between mHealth intervention or no intervention and/or metformin or placebo groups at week 12.
- Difference in HOMA-IR between mHealth intervention or no intervention and/or metformin or placebo groups at week 12.
- Difference in urine and plasma estradiol between mHealth intervention or no intervention and/or metformin or placebo groups at week 12.
- Difference in urine and plasma estrogen metabolites between mHealth intervention or no intervention and/or metformin or placebo groups at week 12.
- Difference in plasma lipid profiles between mHealth intervention or no intervention and/or metformin or placebo groups at week 12.
- Difference in plasma free fatty acid profiles between mHealth intervention or no intervention and/or metformin or placebo groups at week 12.
- Difference in plasma acylcarnitine profiles between mHealth intervention or no intervention and/or metformin or placebo groups at week 12.

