1.10 Study Arm Assignment, Randomization, and Subject Retention

Participants will be assigned to either intervention, both interventions, or no intervention arms after the run-in period in a random manner until 40 participants are enrolled into each arm. Permuted block randomization stratified by WHO functional class (I/II vs. III) will be used to ensure approximate balance of treatment groups within each stratum over time. Based on our previous studies in PAH subjects in our catchment area, African Americans will represent approximately 16% of the study population. Randomization will be performed in small blocks, which vary in size. Investigators will be unaware of the size or order of the blocks. Projected dropout during the 12 week study has been incorporated into the power calculations. The Data Safety Monitor Board may be unblinded at any time to investigate possible adverse events. Procedures for reporting adverse events are outlined in section 7.0.

The group randomization code will be maintained by the research coordinator. The code is to be broken only if knowledge of group assignment for that subject is required to initiate appropriate therapy of an adverse event (AE) or if the safety of the subject is at serious risk without knowledge of the group assignment. The decision to unmask will be made by the PI and/or Co-PI. The Data Safety Monitoring Board will be notified as soon as possible.

Study Designs

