1.19 Study Visits and Contacts

This study will consist of two visits: screening (-2 week) and week 12. The screening and week 12 visit are both estimated to take approximately 4-6 hours each. Patients will be consented by the PI, a clinical research coordinator, or a research nurse. Patient's written consent and study procedures will take place at the Pulmonary Vascular Disease Clinic (CPVD), the Clinical Research Center (CRC), and Vanderbilt Institute of Imaging Science (VUIIS) at Vanderbilt University Medical Center, Nashville, TN; the

Pulmonary Hypertension Clinic or the Clinical Research and Trials Unit (CRTU) at Mayo Clinic, Rochester, MN; and the Pulmonary Hypertension Program or Clinical Research Unit (CRU) at Cleveland Clinic, Cleveland, OH. There will be no changes to a patient's medication regimen.

Participants at Vanderbilt Medical Center will have the opportunity to participate in a sub study that includes a cardiac and skeletal MR spectroscopy, a noninvasive test measuring fat in the heart and skeletal muscles, and a muscle strength and function test at screening and week 12. The visits will occur at Vanderbilt Institute of Imaging Science (VUIIS). The MR spectroscopy will be performed by an experienced MRI technologist and be overseen by a faculty level imagining scientist.

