1.20 Study Schedule of Endpoints and Procedures

The table below summarizes the study endpoint assessments and procedures.

Table 2. Study Procedures

	Screening	Run-In			Treatment Period				Wash Out	Follow Up
		Week -2 to -4	Week -2	Week -1	Week 1	Week 3	Week 6	Week 9		
Visit #	1								2	
Telephone Call #					1	2	3	4		5
Day#	(-14 to -30 days to Study Hour 0)	-14 to -30	-7 to -23	0	21 ± 3	42 ± 3	63 ± 3	84 ± 5	105 ± 3	119 ± 3
Informed Consent	X									
Run-In		X	X							
Randomization					X					
Wash-Out										X
Follow-Up										X
History And Physical Exam										
Medical/Interim History	X								X	
Symptom Assessment	X				X	X	X	X	X	X
Medications	X				X	X	X	X	X	X
Vital Signs	X								X	
Physical Exam	X								X	
WHO Functional Class	X								X	
Testing										
Phlebotomy	X								X	
Glucose & Insulin	X								X	
Free Fatty Acids & Acylcarnitine Profiles	X								X	
Lipid Profiles	X								X	
Estradiol & Estrogen Metabolites	X								X	
NT-proBNP	X								X	
Metabolomics	X								X	
Amino acids	X								X	

HgbA1c	X							X		
CBC	X							X		
Comprehensive Panel	X							X		
Six Minute Walk Test	X							X		
emPHasis-10 Survey	X							X		
Echocardiogram	X							X		
Cardiac Proton MRS	X							X		
Skeletal Muscle Proton MRS	X							X		
Skeletal Muscle Strength & Function Test	X							X		
Urine Pregnancy Test (women only)	X									
Study Procedures										
Adverse Events				X	X	X	X	X	X	X
Compliance			X	X	X	X	X	X		

Assessments of Efficacy and Outcome Measures

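### The estrogen endpoints pool men, post-menopausal and cycling women, and the plan names neither the screening hormone value nor sex/menopausal group as a covariate, which gives away most of the available power

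*Combined protocol and SAP*

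**What the plan says.** The Protocol Summary lists as a secondary endpoint "Difference in urine and plasma estradiol between mHealth intervention or no intervention and/or metformin or placebo groups at week 12", with a parallel entry for estrogen metabolites. These are secondary aims 13 and 14 of the 41 in section 1.7. Section 1.22.8 d states "Estrogen metabolism we will be evaluated by measuring plasma estradiol (E2) and estrogen metabolites", once at screening and once at 12 weeks.

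For the analysis, section 1.24 says "Continuous endpoints will be analyzed using either two-sample t-test or ANOVA, or non-parametric methods Wilcoxon Rank Sum test or Kruskal-Wallis test". It adds general linear models "adjusting for important covariates such as baseline 6MWD, functional status, age, and study site". Nothing in 1.24 is specific to the estrogen endpoints: no transformation, no screening hormone value, no sex or menopausal term.

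Adults aged 18 or older are eligible, with no criterion on sex, menopausal status or hormone use. Table 2 has a row for "Urine Pregnancy Test (women only"), so both sexes, and women who may be cycling, are expected. Section 1.10 says "Permuted block randomization stratified by WHO functional class (I/II vs. III) will be used"; sex is not a stratum. Sex appears in the analysis plans only as a descriptor in the responder comparison of 1.22.12. Neither the visit lists nor Table 2 asks for the last menstrual period, although medications are reviewed at both visits.

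**The concern.** Estradiol differs several-fold between men, post-menopausal women and cycling women, and within a cycling woman by day of cycle. If these groups are pooled and compared at week 12 without a term that separates them, most of the residual variance is hormonal status, which has nothing to do with treatment. The information needed to remove much of it is already collected, namely the screening assay, sex, age, history and medications, but the plan does not commit to using it.

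At stake are two secondary aims with their own plasma and urine collection and mass spectrometry. As written, a moderate treatment effect would probably be missed, and a null result would say little.

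**Working it through.** **The plan's own figure.** The only sample-size calculation is for the primary composite (section 1.26): 40% v 73%, 80% power, alpha 0.05 (taken as two-sided). With pooled proportion 0.565:

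n = [1.96·√(2·0.565·0.435) + 0.8416·√(0.40·0.60 + 0.73·0.27)]² / 0.33² = (1.374 + 0.556)² / 0.1089 ≈ 34.2, i.e. 35 per group.

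This reproduces. The documents give no SD, effect size, sex mix or menopausal mix for estradiol, so every hormone figure below is an assumption.

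**Check 1: power by simulation, 35 v 35, true 25% reduction, two-sided 0.05.**

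Assumptions:
- Geometric mean 25 pg/mL in men and 8 pg/mL in post-menopausal women, with log SD 0.40 and test-retest correlation about 0.75.
- Cycling women log-uniform on 30-350 pg/mL, with screening and week-12 values unrelated (the worst case for baseline adjustment).
- 25% men; cycling women 20-40% of all subjects.

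| Analysis | Power |
|---|---|
| t-test, raw scale | 8-13% |
| Wilcoxon | 15-23% |
| Log ANCOVA on screening value, all subjects | 44-69% |
| Same, plus three-level sex/menopausal group | 59-79% |

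With no true effect, each method rejected in about 4-6% of trials.

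**Check 2: where the variance lies.**

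Assumptions: geometric means 90 (cycling), 8 (post-menopausal) and 25 (men) pg/mL; between-person log SD 0.4; within-person log SD 0.3; cycle amplitude 0.6-0.9 log units; 28-day cycle; samples 98 days apart; cycling/post-menopausal/men mixes of 20/60/20, 40/35/25 and 10/60/30.

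Variance not due to group or phase is 0.4² + 0.3² = 0.25. Total week-12 log variance V is 0.90-1.51. The share due to sex, menopausal status and cycle phase is therefore 1 - 0.25/0.90 = 72% to 1 - 0.25/1.51 = 83%.

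The ratio of geometric means detectable with 80% power is exp(2.80·√(2V/35)). For example, V = 1.51 gives exp(2.80·0.294) = 2.28.

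| Adjustment (log scale) | Residual V | Detectable ratio |
|---|---|---|
| None | 0.90-1.51 | 1.89-2.28 |
| Sex only | 0.77-1.51 | 1.80-2.27 |
| Screening value | 0.23-0.71 | 1.38-1.76 |
| Sex/menopausal group | 0.27-0.41 | 1.41-1.54 |
| Both | 0.19-0.41 | 1.34-1.54 |

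A 25% reduction is a ratio of 1/0.75 = 1.33. Unadjusted, the detectable reduction is 1 - 1/1.89 = 47% to 1 - 1/2.28 = 56%. With both terms it is 1 - 1/1.34 = 25% to 1 - 1/1.54 = 35%. The log scale alone, or a sex term alone, changes little.

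**The case against.** The plan is more open than a bare list suggests. The covariates in 1.24 are given as examples, age is among them and is a partial proxy for menopause, and a rank test is allowed. This stands in part, and the linear model with age was not simulated. But an open list leaves the choice to be made after the data are seen, and age separates neither men from women nor users of hormones from non-users.

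The hormone inputs are assumed, and only plasma estradiol was modelled; urine and the metabolites were not. That stands. The ordering of the methods is more secure than the percentages.

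Four stronger readings are tempting and are not supported:

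- **The visit spacing spoils the comparison.** Screening at day -14 and week 12 at day 84 are 98 days apart, or 3.5 cycles of 28 days, so a reader might infer that cycling women are sampled at opposite phases. The endpoint is a between-arm contrast at week 12, which the gap since screening does not enter. Table 2 also allows 93-119 days (79 + 14 to 89 + 30), or 3.3 to 4.25 such cycles, a range that includes exactly in phase.
- **Baseline adjustment would not help.** It may tell little within cycling women, but across the whole sample it separates high from low estradiol. In check 2 it removes 53-75% of the variance even at exactly 98 days.
- **The endpoints cannot show an effect, or will show false ones.** Power is low, not zero. Randomised imbalance is already covered by the type I error, which stays near 5%.
- **Cycling women should be left out.** Power in men and non-cycling women alone is 91-98% under the assumptions of check 1, but that answers a question about a different population. Adjustment keeps everyone and recovers much of the loss.

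**Conclusion.** The point holds as a matter of efficiency and pre-specification. The plan pools hormonally distinct groups, and it commits neither to the log scale nor to the two covariates that matter most for these endpoints. Under the stated assumptions, the unadjusted tests have 8-23% power for a 25% reduction in plasma estradiol, against 59-79% for a log-scale model with the screening value and sex/menopausal group. The estimate is not biased, and neither the primary endpoint nor the sample size is touched. This is a minor but nearly free improvement to two secondary aims of a phase II trial.

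**What to change.** Add to section 1.24, before the estrogen data are analysed: estradiol and estrogen metabolites, in plasma and urine, are analysed on the log scale in all subjects with a week-12 value, by a linear model with treatment arm, the log screening value and a sex/menopausal/hormone-use group. Define that group in advance from sex, age, medical history and the medication review already done at both visits. Report men and non-cycling women as a sensitivity analysis. For subjects still to be seen, record the last menstrual period at both visits.

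The cost is a few model degrees of freedom, one history question per visit and a short SAP amendment. For subjects already seen, the group would have to be derived from existing records, so some misclassification is possible.
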